Using Imaging to Assess Effects of THC on Brain Activity (fNIRS)

Statistical Analysis Plan

The fNIRS Team

Version 1

First version: 4/29/2022

Latest version: 4/29/2022

ClinicalTrials.gov ID: NCT03655717

Unique protocol ID: 2015P001516

U.S. NIH Grant/Contract Award Number: R42DA043977

Table of contents

Table of contents	2
Glossary	3
Study Design	4
Participants.....	4
Analytic Approach.....	5
Primary Outcomes.....	5
Statistical Model	5
Covariates	6
Missing Data.....	6
Sample Size Determination	7
Software.....	8
References	9

Glossary

Abbreviation	Label
ETOH	Alcohol
FDA	Federal Drug Administration
fNIRS	Functional near-infrared spectroscopy
HbO	Oxygenated hemoglobin
PFC	Pre-frontal cortex
THC	Tetrahydrocannabinol

Study Design

This study will assess the effects of THC intoxication using dronabinol (synthetic THC) on the HbO signal during resting state and task-based activation in the prefrontal cortex (PFC), resting state connectivity, neurocognitive task performance, clinical signs of intoxication, and correlations between these measurements. Participants will be given up to 80 mg of dronabinol, an FDA-approved synthetic form of THC that is used to treat loss of appetite that causes weight loss in people with AIDS. THC is the principle psychoactive drug in marijuana. The study will be conducted in regular cannabis users who present at the screening visit with a positive urine screen for THC metabolites. Data will be collected over two phases:

- Phase 2A is a randomized, double-blind, placebo-controlled, study of effect of dronabinol vs placebo. This phase will investigate the effect of THC on fNIRS brain signature and its association with self-reported intoxication, laboratory measures of impairment, and the gold-standard behavioral field test of driving impairment used by law enforcement.
- Phase 2B is a randomized, double-blind, placebo-controlled, 2 by 2 crossover study of effect of dronabinol, ethanol, and combined dronabinol and ethanol on brain activation and connectivity as measured by fNIRS. Phase 2B will examine potential interaction between THC and alcohol following co-administration of THC with oral ethanol exposure in healthy volunteers.

Participants

Participants will be 150 adults who use marijuana at least monthly (aged 18-55) will be recruited to participate in this study.

Analytic Approach

Primary Outcomes

The primary outcomes for the study will be...

1. The mean HbO level averaged over the duration of the N-back task scan (approximately 2938 samples taken over 376 seconds in 128 millisecond intervals).
2. The mean HbO level averaged over the duration of the resting state scan (2814 samples taken over 360 seconds in 128 millisecond intervals).

Mean HbO levels for both outcomes will be determined over (a) four conditions administered over separate visits about a week apart (where participants could be dosed with placebo, THC only, ETOH only, or both THC and ETOH), and (b) two scans per condition: A scan prior to and approximately 100 minutes after being dosed. Higher HbO levels indicate a greater degree of neural activity in the PFC regions of the brain.

Statistical Model

We will analyze both primary outcomes using a multi-level linear regression model with subject-varying intercepts estimated via maximum likelihood. The key exposures are whether a person was dosed with placebo, THC, ETOH, or the combination of THC and ETOH. Table 1 lists the numeric coding used to test our planned contrasts. All terms will be coded as 0 for pre-dose scans, as no combination of drugs will have been administered.

Table 1: Design matrix for testing key exposures

Scan	Dose	Main effects		Interaction THC x ETOH
		THC	ETOH	
Post-dose	Placebo	0	0	0
	THC	1	0	0
	ETOH	0	1	0
	THC + ETOH	1	1	1

Statistical significance for each contrast will be determined via a non-parametric bootstrap procedure for robustness. First, each subject's set of completed condition (placebo, THC, ETOH, THC + ETOH) will be randomly shuffled across their set of visits. Second, the shuffled data will be refit with the multi-level model, and coefficient estimates will be obtained for the key exposures. Third, the prior two steps will be repeated 10,000 times, providing a null distribution to compare the observed coefficient estimates against. The p-values for the key exposures will be estimated as $P(|o| < |s_i|)$, where o is the observed coefficient, and s_i is the i th coefficient from the shuffled data. For each outcome there will be 3 p-values (the main effects of THC and ETOH and their interaction). The total set of 6 p-values will be adjusted for multiple comparisons using the Benjamini-Hochberg method (Benjamini & Hochberg, 1995). An adjusted p-value < 0.05 will indicate a statistically significant effect of either THC, ETOH, or their interaction on neural activity in the PFC.

Covariates

We will include two sets of covariates in our model. First, we will include a dummy-coded contrast comparing pre-dose scans (coded as 0) to post-dose scans (coded as 1). Second, we will include covariates adjusting for visit order. The referent will be the first visit (coded as -1), and we will include three terms for the second, third, and fourth visit (coded as 1 for the given visit and 0 otherwise). All terms will then be converted to z-scores.

Missing Data

We will only include data from complete visits with both pre-dose and post-dose scans. Participants with no complete pairs of pre and post-dose scans for any conditions will be excluded from the analyses. Missingness will be naturally handled by the multi-level modeling approach, as the higher order terms governing the random effects provide shrinkage and information even in the presence of missing cases (Baayen, Davidson, & Bates, 2008).

Sample Size Determination

Sample size was pre-specified in our grant application. Since no prior studies have attempted to predict impairment using fNIRS measurements, we did not have an effect estimate with which to determine sample size. In order to maximize the chance that standard methods could detect an effect of intoxication on PFC activation patterns with the N-Back task, we collected as many scans as possible with the R42 grant funds allotted.

Software

All analyses will be done using the statistical software R (version 4.1.1; R Core Team, 2021) and integrated development environment RStudio (version 2020.9.0.351; RStudio Team, 2021). Data will be prepared using the R packages 'dplyr' (version 1.0.7; Wickham, François, Henry, & Müller, 2021). Models will be fit using the R package 'lme4 (version 1.1-27.1; Bates, Maechler, Bolker, & Walker, 2015).

References

Baayen, R. H., Davidson, D. J., & Bates, D. M. (2008). Mixed-effects modeling with crossed random effects for subjects and terms. *Journal of Memory and Language*, 59 (4), 390-412.
<https://doi.org/10.1016/j.jml.2007.12.005>

Benjamini, Y., & Hochberg, Y. (1995). Controlling the false discovery rate: a practical and powerful approach to multiple testing. *Journal of the Royal Statistical Society: Series B (Methodological)*, 57 (1), 289-300. <https://doi.org/10.1111/j.2517-6161.1995.tb02031.x>.

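### Does the SAP's single primary model mix Phase 2A and Phase 2B scans, so that differences between the phases bias the ethanol and interaction tests?

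*SAP*

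**What the plan says.** Under Study Design the SAP announces that "Data will be collected over two phases". Phase 2A compares dronabinol with placebo; Phase 2B is the two-by-two crossover with ethanol. The Participants paragraph then gives one count for the whole study: "Participants will be 150 adults who use marijuana at least monthly (aged 18-55) will be recruited to participate in this study".

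Under Primary Outcomes, both outcomes are taken over "four conditions administered over separate visits about a week apart", with two scans per condition: "A scan prior to and approximately 100 minutes after being dosed". Under Statistical Model: "We will analyze both primary outcomes using a multi-level linear regression model with subject-varying intercepts estimated via maximum likelihood". Table 1 has four post-dose rows, two of them with ethanol.

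Under Covariates: "We will include two sets of covariates in our model". One is pre-dose against post-dose. The other is visit order, for which "we will include three terms for the second, third, and fourth visit". There is no term for phase. Under Missing Data: "Participants with no complete pairs of pre and post-dose scans for any conditions will be excluded from the analyses".

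**The concern.** The SAP introduces two phases, gives one unsplit number and one model, and does not connect them. The missing-data rule asks only for a complete pair of scans in some condition, which a Phase 2A participant would have. No separate analysis of 2A is described. A reader could therefore suppose that all scans from both phases go into one fit.

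That would matter because ethanol is given only in 2B, so phase is partly confounded with the ethanol columns of Table 1. Phase 2B also has a placebo drink, a venous catheter and a slightly later scan. Any phase difference in response would have to go into the treatment coefficients. Four of the six primary p-values (ethanol and interaction, for two outcomes) depend on 2B, and the interaction is that phase's stated purpose. The n behind those four tests is not given.

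**Working it through.** **1. The stated figure.** The 150 cannot be reproduced. Under Sample Size Determination the SAP gives no effect size, SD or power; it says that n came from the grant application and that as many scans were collected as funds allowed. It can only be set against other counts. The protocol has 200 in Phase 2A, 200 in Phase 2B, and a ceiling of 200 for Phase II under Study endpoints. Since 150 < 200, no ceiling is breached.

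**2. The primary analysis beside the two phases.**

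| Feature | SAP | Protocol 2A | Protocol 2B |
|---|---|---|---|
| Conditions per participant | 4 | 2 | 4 |
| Dosing visits | 4 (terms for visits 2 to 4) | 2 | 4 |
| Ethanol | in Table 1 | none | yes |
| Post-dose scan | about 100 min | about 90 min | about 100 min |
| Age | 18-55 (for the 150) | 18-55 | 21-55 |

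The first four rows describe the analysis and match 2B. The age row belongs to the recruitment count and spans both phases, as a two-phase total should.

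**3. What pooling would do to the interaction.** Assumptions not in the documents: splits of 50/100, 75/75 and 100/50, residual SD 1, complete data, balanced orders, nobody in both phases. Let d be the THC effect in 2B minus that in 2A, T the THC effect in 2B, and w = n_A/(n_A + n_B).

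- The THC coefficient comes from THC against placebo, to which both phases contribute: T - w·d.
- The THC effect in the presence of ethanol comes from 2B only: T, if there is no true interaction.
- Interaction = T - (T - w·d) = w·d.
- Pooled SE of the interaction = √(2/n_B + 2/150). With 2B only it is √(4/n_B).

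| Split 2A/2B | w | Pooled SE | d that moves the interaction by one SE (SE/w) | SE, 2B only |
|---|---|---|---|---|
| 50/100 | 0.333 | √(0.0200 + 0.0133) = 0.183 | 0.55 | 0.200 |
| 75/75 | 0.500 | √(0.0267 + 0.0133) = 0.200 | 0.40 | 0.231 |
| 100/50 | 0.667 | √(0.0400 + 0.0133) = 0.231 | 0.35 | 0.283 |

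A generalised least squares calculation of the SAP model gives the same shares and SEs.

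**4. What pooling would do to ethanol.** From the same calculation, with an intraclass correlation of 0.2 to 0.8, the ethanol coefficient takes up 0.19-0.25, 0.30-0.37 and 0.41-0.50 of a 2B-minus-2A difference in pre-to-post change for the three splits. The shuffle test still holds its level, because the shuffled coefficients carry the same bias. With a difference of 0.5 and an intraclass correlation of 0.5, simulated rejection was 4.6% to 5.2% for all three terms.

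**5. With 2B only.** Phase is constant, so every leak is zero. In a simulation with 75 participants in 2B, total SD 1, THC effects of 0.2 (2A) and 0.5 (2B) and no true interaction, the interaction test rejected 3.2% of the time. Pooling in a further 75 from 2A gave 14.8%.

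**6. Reading the error rates.** A bias of exactly one SE makes any two-sided 5% z-test reject with probability P(Z > 0.96) + P(Z < -2.96) = 0.169 + 0.002, about 17%. That follows from the size chosen for the bias. The SAP decides on Benjamini-Hochberg over six p-values. At 0.05/6 = 0.0083 (critical value 2.638) the same bias gives P(Z > 1.638), about 5%. If two other tests already pass, the threshold is 3 × 0.05/6 = 0.025 (critical value 2.241), which gives about 11%.

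**The case for a change.** The best case for a change is that a pre-specified plan should not leave its analysis set to inference. The shuffle uses each participant's completed conditions, the missing-data rule is not tied to a phase, and 2A has no other stated analysis, so two analysts could choose different data. The unstated 2B n also matters: with 80% power and an unadjusted two-sided 5% test, the detectable interaction is 2.8016 × √(4/n), which is 0.46 residual SD at n = 150 and 0.79 at n = 50. The protocol lets a person join both phases, giving 2 + 4 = 6 dosing visits where the SAP codes four.

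The omission is real, and so is the silence on 2A. The rest carries less weight:

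- The complete-pair rule excludes people with missing scans. It makes full sense for 2B participants who miss visits, and it does not define who belongs in the analysis.
- The SAP describes 2A largely through associations with self-reported intoxication, laboratory impairment and the field test. None of these is a primary outcome, so silence about 2A under the primary model does not imply pooling.
- The 2B n affects power, but stating it would not alter power or any estimate.
- The six-visit problem needs pooling, overlap and a single shuffle set together, and nothing says that any of these happens.
- The only documented source for a different THC effect is a scan at about 90 rather than about 100 minutes. The protocol's Phase 1 procedure places both times in one window of 90 to 150 minutes. Its risk section gives a peak at 2 to 4 hours, which both times precede. The 2B procedure takes dronabinol administration from 2A. Nothing links ten minutes to a difference of 0.35 to 0.55 residual SD.

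Nor is there a simple safeguard to gain. In a pooled fit, adding phase and phase-by-post terms would leave the interaction share at 33%, 50% or 67%. It would also raise the share of a THC-effect difference that reaches ethanol from 4-13% to 17-33%.

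**Conclusion.** No change follows. The SAP leaves out one sentence on its analysis set, but its outcome definitions, scan time, visit terms and Table 1 all fit Phase 2B, and on that reading the phase bias is exactly zero. The 150 remains a valid recruitment total for the two-phase study, and the participants in each analysis can be counted from the collected scans. The protocol's figures of 200, 200 and a ceiling of 200 for Phase II are enrolment limits, with people in both phases counted twice; they alter no result.

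The leak of 0.33 to 0.67 of a phase difference into the interaction, and of about 0.2 to 0.5 into ethanol, is correct arithmetic for a pooled fit under assumed splits and correlations. It illustrates a reading that the text does not favour, multiplied by a phase difference that no document gives. The conclusion rests on the 2B reading and would need another look only if 2A scans were in fact pooled.

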participants will also provide a urine sample which will be tested for drugs and pregnancy (if applicable) to ensure participants are positive for THC. Participants are trained on the driving simulator computer tasks. If participants are determined to be eligible, they will be scheduled for the following two visits. In a double-blind, placebo-controlled, random order cross-over study of single dose THC (dronabinol) at physician determined doses of 10-80mg, participants will receive THC capsules or identical placebo on two separate study visits, randomized for order. The MGH research pharmacy will generate a blinded randomization code for order of dosing and will dispense blinded drug in the dose ordered and identical placebo for use on separate study days. In order for a complete washout of effects, and to minimize the effect of repeat testing for the neuropsychology tasks, study visits must be at least 1 week apart. On each study day, participants will have a light standardized breakfast after overnight fast and sleep. They will be asked not to deviate from normal behaviors (e.g. if they drink caffeinated beverages or smoke cigarettes in the mornings, they will be asked to do so on the study day so that no symptoms of caffeine or nicotine withdrawal will appear during the scanning period. On each study day, participants will undergo baseline fNIRS testing (see above “Cognitive Tasks during FNIRS testing”), substance use history interview (timeline follow back), two sets of baseline vital signs, a driving simulator computer task refresher, and several questionnaires (HADS, URGE, PSQI, CWS). Dronabinol or placebo will be administered once morning procedures are complete, after which point heart rate, blood pressure, and responses to DEQ and BAES questionnaires will be monitored at 20 minute intervals. The second fNIRS session will be conducted at approximately 90 minutes post dose, followed by driving simulator computer tasks. A field test of sobriety will be conducted immediately following the second fNIRS assessment. The third fNIRS session will be conducted at approximately 220 minutes post dose, prior to participant discharge. See Below for schematic:

Subjects who participated in Phase 1 will be eligible for Phase 2, but enrollment in Phase 1 is not a requirement for Phase 2. Therefore, new subjects who have not completed Phase 1 will also be eligible for Phase 2.

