Vanderbilt University, with collaboration from a consortium of institutional partners, has developed a software toolset and workflow methodology for electronic collection and management of research and clinical trial data. REDCap (Research Electronic Data Capture) data collection projects rely on a thorough study-specific data dictionary defined in an iterative self-documenting process by all members of the research team with planning assistance from Partners HealthCare Research Computing, Enterprise Research Infrastructure & Services (ERIS) group. The REDCap Survey is a powerful tool for building and managing online surveys. The research team can create and design surveys in a web browser and engage potential respondents using a variety of notification methods. Both REDCap and REDCap Survey systems provide secure, HIPAA compliant, web-based applications that are flexible enough to be used for a variety of types of research, provide an intuitive interface for users to enter data and have real time validation rules (with automated data type and range checks) at the time of entry.

fNIRS Data Analysis

The instrument will acquire raw data for each detector at ~40 kHz. The individual source signals then will be obtained with a digital bandpass filter – for example, a discrete Fourier transform or an infinite-impulse-response filter. The individual source signals will be separated off-line with an infinite-impulse-response filter with a 50 Hz band pass frequency. Next, the time series pairs from each detector will be converted from wavelength (absorption) to relative concentrations (of oxy-/deoxy-hemoglobin). This will be done with the modified Beer-Lambert Law and the absorption coefficients of oxy- and deoxy-hemoglobin (HbO and Hb, respectively) [34]. (The near-IR wavelengths are chosen because oxy-/deoxy-Hb are the predominant absorbers in the tissue at these wavelengths.) The result will be an oxy-Hb and deoxy-Hb timeseries associated with each source-detector pair.

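### The primary model has no visit-level term, so each visit's pre-dose scan is not used as that visit's baseline; precision may be lost, materially only if same-visit correlation is about 0.5 or more

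*SAP*

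**What the plan says.** The SAP's Statistical Model section gives one random effect: "We will analyze both primary outcomes using a multi-level linear regression model with subject-varying intercepts estimated via maximum likelihood". Under Primary Outcomes, each outcome is measured in "two scans per condition: A scan prior to and approximately 100 minutes after being dosed", with visits about a week apart. Both scans enter as outcome rows. For the drug terms, "All terms will be coded as 0 for pre-dose scans, as no combination of drugs will have been administered".

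The Covariates section adds two things. The first is a single pre/post indicator: "we will include a dummy-coded contrast comparing pre-dose scans (coded as 0) to post-dose scans (coded as 1". The second is three visit-order terms shared by all participants. The Missing Data section keeps only visits with both scans, so every analysed visit has its own pre-dose scan.

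Significance comes from a reference distribution in which each subject's "set of completed condition (placebo, THC, ETOH, THC + ETOH) will be randomly shuffled across their set of visits", with the model refitted 10,000 times. Neither document specifies a visit-within-subject effect, a change score or a same-visit baseline covariate.

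**The concern.** A participant's HbO level may differ from one week to the next for reasons unrelated to the drug. If so, both scans of a visit move together, and the pre-dose scan shows how far that visit was shifted. The planned model cannot use this. Its subject intercept is an average over all visits, its pre/post term is common to everyone, and its visit-order terms describe average drift only. A visit-level shift is therefore left in the residual.

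This affects all six primary tests (three contrasts on two outcomes). The trial has no power calculation to fall back on: the SAP's Sample Size Determination section says there was no effect estimate and that "we collected as many scans as possible with the R42 grant funds allotted". Information in scans already paid for might go unused.

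**Working it through.** **Inputs from the documents.** Two scans per visit; four visits per participant in Phase 2B and two in Phase 2A; the Table 1 coding; one pre/post indicator; three visit-order terms; 150 participants (SAP, Participants). No standard deviation, effect size, power or rho is stated, so there is no figure of the plan's own to reproduce.

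**Assumptions.** Within-subject variance is set to 1 and split into a visit part (rho) and a residual part (1 − rho). Rho is the correlation remaining after the subject effect. A raw pre/post correlation that is wholly between subjects costs nothing, because the subject intercept already removes it. Sequences are taken as a Williams design.

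**Closed form, complete four-visit data, equal response in all subjects.** Under the plan, THC versus placebo reduces to the within-subject difference of the two post-dose scans; the matching pre-dose scans drop out.
- Plan, variance per subject: 1 + 1 = 2, whatever rho is.
- With a visit intercept, rho times the pre-dose difference is subtracted: 2(1 + rho² − 2·rho·rho) = 2(1 − rho²).
- Ratio: 1 − rho². At rho 0.2, 0.3, 0.5, 0.7 this is 0.96, 0.91, 0.75, 0.51. It is the same for ETOH and the interaction.
- Plain change score, for comparison: 4(1 − rho). This is worse than the plan below rho 0.5 and better only above it.

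**When subjects differ.** The protocol makes some variation in response likely: "single dose THC (dronabinol) at physician determined doses of 10-80mg", a dose choice that Study Drug and Dosing calls inexact, and effects that Risks and Discomforts describes as differing between patients. The drug-free change from the first scan to the second may also differ between subjects, and the plan has only one common term for it. The table gives large-sample variances (sandwich form, maximum likelihood variance components) for nested model over plan, THC contrast. Added variances are multiples of the within-subject variance.

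| What varies between subjects | rho 0.3 | rho 0.5 | rho 0.7 |
|---|---|---|---|
| Nothing (most favourable) | 0.91 | 0.75 | 0.51 |
| THC response, 0.5–1 | 0.93–0.94 | 0.80–0.84 | 0.61–0.69 |
| THC and ETOH response, 1 each | 0.95 | 0.86 | 0.72 |
| Pre-to-post change, 0.5–1 | 0.93–0.98 | 0.78–0.84 | 0.55–0.63 |
| THC response and pre-to-post change, 1 each | 1.00 | 0.92 | 0.79 |
| THC, ETOH and pre-to-post change, 1 each | 1.00 | 0.94 | 0.83 |

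The gain shrinks down the table because subject-specific changes make pre- and post-dose scans look less alike. The visit variance is then estimated low, and the nested fit moves back towards the plan. An assumed mix of 75 four-visit and 75 two-visit participants with THC response variance 1 gives 0.94, 0.84 and 0.69, so including Phase 2A does not alter the THC result.

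**In participants and power.** The plan needs 1/factor times the participants for equal precision. Its power is Φ(2.8016·√factor − 1.96) for a THC effect with 80% nominal two-sided power under the nested model. The ends of the range are:
- rho 0.3: 1/0.91 = 1.10 down to 1.00 times; 76% to 80%.
- rho 0.5: 1/0.75 = 1.33 down to 1/0.94 = 1.06 times; 68% to 78%.
- rho 0.7: 1/0.51 = 1.96 down to 1/0.83 = 1.20 times; 52% to 72%.

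**Validity of the shuffle.** In simulation (1,000 data sets per setting, 199 whole-visit shuffles, nominal 5%), rejection with no drug effect was 4.2–6.0% under the plan and 4.4–6.2% under the nested model. With a real THC effect, null ETOH and interaction tests rejected at 1.7–5.1% (plan) and 0.7–5.8% (nested). The Monte Carlo error is about 0.7 points.

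**The case against.** The strongest reply is that no error has been shown. Treatment order is randomised, the shuffle keeps each visit's pair of scans together, and the plan sets no power target that it could miss. This stands: the point is about efficiency. A reader might infer that omitting the visit effect biases the drug estimates or inflates false positives; the randomised order and the rejection rates above do not support that.

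Next, rho is unknown. The protocol's fNIRS Data Analysis section says "the time series pairs from each detector will be converted from wavelength (absorption) to relative concentrations". If those values are referenced within each scan, which is not stated, rho could be low, and at 0.2 or less at most 4% of variance is at stake. This also stands. A reader might infer that a loss is certain, or that rho of about 0.3 is enough to matter. The documents do not show what rho is. The 9% gain at 0.3 needs equal response and an equal pre-to-post change in everyone, and it vanishes when both vary strongly.

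Third, fixing the nested model at 80% power puts the comparison on the steep part of the curve. With 150 four-visit participants and equal response, the THC effect detectable with 80% power is 2.8016·√(2/150) = 0.32 within-subject SD under the plan, against 0.31 at rho 0.3 and 0.28 at rho 0.5. At 0.4 SD the plan already has 93%. That is fair, and the variance ratios are the better summary.

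What survives is that the nested model never had a larger large-sample variance than the plan in any case examined. In smaller-sample simulation with rho estimated, the ratio at rho of 0.1 or less was 0.996 to 1.003. Trying it therefore costs almost nothing in precision.

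**Conclusion.** The concern holds as a conditional loss of precision. The planned model leaves visit-level HbO shifts in the error of all three drug contrasts although each analysed visit carries its own pre-dose scan. For THC, the variance that a visit intercept would remove is nil to about 9% at rho 0.3, about 6–25% at rho 0.5 and about 17–49% at rho 0.7. It becomes material from about rho 0.5.

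These ranges rest on assumed values of rho and of between-subject variation (up to 1 times the within-subject variance for each source) and on a balanced sequence design. Whether precision is in fact lost cannot be settled from the documents. Nor does the SAP's past-tense account of scan collection show that outcome results had been seen when the model was chosen.

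**What to change.** Fit (1 | subject/visit) in lme4 with the fixed effects unchanged, in both the observed and the shuffled fits. Keep the visit-level shuffle and the complete-pair data set. A plain change score is not a safe substitute, since it loses precision below rho 0.5 even with equal response.

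Report the estimated visit variance, so that readers can see whether the term mattered. State that varying drug response or a varying pre-to-post change makes the implied rho read low; in simulation with varying THC response it averaged 0.38 when the true value was 0.5.

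If primary results have already been seen, leave the primary model as it is and report the nested fit as a labelled sensitivity analysis.

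The cost is one more variance component and longer run time over 10,000 shuffles. Some fits may be singular, with the visit variance at zero; those fits equal the current model.
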